1.3 Risks and benefits assessment

Risks:

1. Perioperative risks related to the surgeries: bleeding, wound infection, adjacent organ injury, wound dehiscence

2. Fail to perform the surgery successfully with SP system: conversion to multiport robotic or traditional endoscopic surgery or open surgery

Potential Benefits:

1. Cosmetic benefit: single incision or fewer scars at belly

Study: TASP-UTUC

Version: 1

Date: 17/10/2024

NTUH Clinical Trial Protocol

2. Peri-operative benefits: shorter hospital stays, less complication, less pain and less analgesic use, less CO₂ retention and oxidative stress related to pneumoperitoneum, improvement of disease symptoms and quality of life.

1.4 Regulatory

This study will be conducted in compliance with the protocol approved by the Institutional Review Board (IRB) / Research Ethics Committee (REC) of NTUH, and according to Good Clinical Practice standards and per Taiwan Health Authority regulations. No deviation from the protocol will be implemented without the prior review and approval of the IRB except where it may be necessary to eliminate an immediate hazard to a research subject. In such case, the deviation will be reported to the IRB as soon as possible.

2. Objectives and Endpoints

2.1 Study objectives

2.1.1 Primary objective

To investigate clinical feasibility of radical nephroureterectomy(RNU) and bladder cuff resection(BCR) using single-port robotic surgery

2.1.2 Secondary objectives

To evaluate safety, surgical outcomes, patient characteristics, and patient-reported outcomes of radical nephroureterectomy(RNU) and bladder cuff resection(BCR) using single-port robotic surgery

2.1.3 Other exploratory objectives (if any)

Not applicable

2.2 Study endpoints

2.2.1 Primary endpoint

Successful completion of RNU+ BCR without conversion to alternative surgery

2.2.2 Secondary endpoints

- Operative time (first skin incision to closure of wound)
- Console time
- Transfusion and estimated blood loss
- Length of hospital stay
- Complication (rate, in 30 days) (intraoperative and/or postoperative) (Clavien system)
- Readmission (rate, in 30 days)
- Reoperation (rate, in 30 days)
- Perioperative mortality (in 30 days)
- Pain score

2.2.3 Other exploratory endpoints (if any)

Not applicable

Study: TASP-UTUC

Version: 1

Date: 17/10/2024

NTUH Clinical Trial Protocol

3. Study Design

3.1 Overall design

This prospective, interventional, non-randomized, single arm, clinical trial will investigate feasibility and safety of robot-assisted radical nephroureterectomy (RNU) + BCR using da Vinci SP Surgical System in Taiwan and provide initial evidence of retroperitoneal approach. All the investigators are well trained and have received proof of training after completing the training program for da Vinci SP system provided by Intuitive. This study includes single-arm supine anterior retroperitoneal approach (SARA) by single-port robotic natural orifice transluminal endoscopic surgery.

This study will be conducted in National Taiwan University Hospital, Taipei.

Informed consent will be provided to patient who has an indication of radical nephroureterectomy (RNU)+ BCR. Study participants will sign an informed consent before any study procedure begins. Eligibilities will be assessed during screening period (2 weeks) with blood test and other routine assessments. Eligible patient will undergo surgical intervention using da Vinci SP Surgical System. Post-operation follow-up will be performed according to time points specified in the study calendar.

3.1.1 Recruitment plan

This trial plans to recruit 20 evaluable patients at single trial site, NTUH. Assuming screening failure and drop-out of 5 patients, at least 25 patients will be screened (enrolled). Recruitment is estimated to complete within 1 year with recruitment rate of 0.5 patient per week.

Study: TASP-UTUC

Version: 1

Date: 17/10/2024

NTUH Clinical Trial Protocol

3.2 Study calendar

Period	Screening	Operation period				Follow-up period	
		Operation	POD 1	Discharge day	Follow-up 1	Follow-up 2	Follow-up 3
Visit	Screening visit						
Day (window time)	-14 ~-1	0	1	n.a.	30 (± 7)	90 (± 14)	180 (± 14)
Informed consent	X						
Medical history	X						
CBC D/C	X						
Biochemistry	X						
Other safety blood test	X						
Pre-operation routine test and imaging	X						
Operation		X					
Peri-operative outcomes		X	X	X			
Concomitant medications	X		X	X	X		
Analgesics use	X		X	X			
Pain assessment	X		X	X			
AE / Complication	X	X	X		X	X	X
Patient-reported outcomes	X		X		X		

Footnotes:

- POD: post-operation day
- CBC D/C: Complete blood count with differential count
- AE: adverse event

3.3 Criteria of Termination of the Trial

The trial shall be terminated by the investigator or the IRB when deemed necessary after evaluation. Incidents that may cause the termination of the trial include the encounter of life-threatening AE, fatal AE, serious non-compliance, etc. If 2 mortalities or 5 severe morbidities occur during the trial, the investigator will terminate the trial. A detailed written explanation of the reasons for the termination needs to be given to IRB and Health Authority as appropriate.

4. Study Population

4.1 Inclusion criteria

1. Age 20 years or more
2. Histologically or cytologically diagnosed upper tract urothelial cancer
3. indication of radical nephroureterectomy and ipsilateral bladder cuff resection, deemed feasible for robotic surgery
4. ASA physical status classification 1-2 and adequate organ function
5. Patients willing and able to comply with study protocol requirements and follow-up
6. With informed consent

4.2 Exclusion criteria

1. Synchronous bladder cancer
2. Distant metastasis of cancer
3. BMI ≥ 30 or BMI < 18.5
4. Unable to tolerate lateral decubitus or Trendelenburg position (relative)
5. Severe adhesion due to prior abdominopelvic surgery
6. Previous radiation treatment to the pelvic area
7. Active infectious disease
8. Severe concomitant illness that drastically shortens life expectancy or increases risk of therapeutic interventions, such as: Severe heart disease (NYHA functional class III-IV) or Severe lung disease (GOLD Group C-D)
9. Can't follow trial-required procedures
10. Concomitant systemic or pelvic disease that increases the risk of surgery
11. Long-term use of anti-coagulant(s)
12. Patients with coagulopathy
13. Emergency surgery

4.3 Withdrawal criteria

1. Patients refuse to continue follow up per protocol during the study period
2. Patients developing mortality or morbidity during or within 30 days after the surgery that do not have consequential correlations with the surgical procedures (such as those resulting from natural disaster, war, or unexpected accidents)

5. Treatment

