	
8. Severe concomitant illness that drastically shortens life expectancy or increases risk of therapeutic interventions, such as: severe heart disease (NYHA functional class III-IV) or severe lung disease (GOLD Group C-D)9. Cannot follow trial-required procedures10. Concomitant systemic or pelvic disease that increases the risk of surgery11. Long-term use of anti-coagulant(s)12. Patients with coagulopathy13. Emergency surgery
Design of trial:	
• Prospective• Interventional• Open label• Single arm• Study period: 2 years (From Dec/1/2024 to Nov/30/2026)• Study site: single center study
Study treatment:	Radical nephroureterectomy and ipsilateral bladder cuff resection using da Vinci SP Surgical System (robotic surgery)
Primary endpoint:	Success without conversion to alternative surgery
Statistical analysis and sample size estimation:	
• Statistical methods: Descriptive methods will be used.• Interim analysis: No• Efficacy assessment group: Per Protocol• Estimated sample size:
○ Enroll: 25○ Evaluable: 20

Table of Content

Clinical Trial Protocol.....	1
Synopsis	2
Table of Content.....	4
Abbreviations.....	6
1. Introduction	7
1.1 Background and rationale	7
1.1.1 Medical background	7
1.1.2 Animal and preclinical study	8
1.2 Investigational product	8
1.3 Risks and benefits assessment	9
1.4 Regulatory	10
2. Objectives and Endpoints.....	10
2.1 Study objectives	10
2.1.1 Primary objective	10
2.1.2 Secondary objectives.....	10
2.1.3 Other exploratory objectives (if any).....	10
2.2 Study endpoints.....	10
2.2.1 Primary endpoint.....	10
2.2.2 Secondary endpoints	10
2.2.3 Other exploratory endpoints (if any).....	10
3. Study Design.....	11
3.1 Overall design.....	11
3.1.1 Recruitment plan.....	11
3.2 Study calendar.....	12
3.3 Criteria of Termination of the Trial.....	13
4. Study Population	13
4.1 Inclusion criteria	13
4.2 Exclusion criteria.....	13
4.3 Withdrawal criteria.....	13
5. Treatment	14

Study: TASP-UTUC

Version: 1

Date: 17/10/2024

NTUH Clinical Trial Protocol

5.1	Treatment administration	14
5.2	Concomitant therapy	14
6.	Efficacy Assessments	14
7.	Safety Assessments.....	15
8.	Adverse Event Reporting.....	15
8.1	Definitions and reports of adverse events.....	15
8.2	Serious Adverse Events.....	16
8.3	Adverse event follow-up	16
9.	Statistical Considerations.....	16
9.1	Sample size determination.....	16

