5.2 Concomitant therapy

Medical treatment of underlying chronic diseases (such as diabetes or hypertension) is allowed.

6. Efficacy Assessments

- Primary endpoint: Success without conversion to alternative surgery: successful completion of radical nephroureterectomy and bladder cuff resection with da Vinci SP system (no conversion to conventional laparoscopic, multiport da Vinci surgery or open surgery; addition of access port to complete the procedure would not be considered as conversion.)
- Operative time (min): first skin incision to closure of wound
- Console time (min): the time when the surgeon starts the console work till the specimen is taken out from the patient
- Estimated blood loss (mL): measured at operating suite
- Length of hospital stay (day): the duration from operation day to the discharge day (included)
- Pain score: measured by Visual Analogue Scale (VAS)

Other assessments:

- Patient demographics and medical history
- Pathology assessment
- Body mass index, body weight
- Analgesic use/types: opioid or non-opioid, changes in post-operative period)

Study: TASP-UTUC

Version: 1

Date: 17/10/2024

NTUH Clinical Trial Protocol

7. Safety Assessments

- Safety labs (complete blood count and other routine tests)
- Estimated blood loss (mL): measured at operating suite.
- Transfusion: record of blood product received.
- Complication (intraoperative and/or postoperative) (Clavien Dindo grading)
- Readmission (in 30 days)
- Reoperation (in 30 days)
- Perioperative mortality (in 30 days)

8. Adverse Event Reporting

Upon the occurrence of serious adverse events (SAE) which result in serious malfunctioning of the medical device, [name] [name] will report SAEs to the IRB of NTUH according to the Serious Adverse Event Reporting Procedures and Guidelines posted by NTUH. SAE reports to the IRB should include the following information when calling the Medical Monitor:

- Date and time of the SAE
- Date and time of the SAE report
- Name of reporter
- Call back phone number
- Affiliation/Institution conducting the study
- Protocol number
- Title of protocol
- Description of the SAE, including attribution to drug and expectedness

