8.1 Definitions and reports of adverse events

All adverse events that occur after the informed consent is signed (including run-in) must be recorded on the adverse event CRF (paper and/or electronic) whether or not related to study agent. AE Data Elements including:

- AE reported date
- AE Verbatim Term
- CTCAE Term (v 5.0)
- Event onset date and event ended date
- Severity grade
- Attribution to study agent (relatedness)
- Whether or not the event was reported as a Serious Adverse Event (SAE)
- Action taken with the study agent
- Outcome of the event
- Comments

Identify the adverse event using the NCI Common Terminology Criteria for Adverse Events (CTCAE) version 5.0. The CTCAE provides descriptive terminology and a grading scale for each adverse event listed.

Study: TASP-UTUC

Version: 1

Date: 17/10/2024

NTUH Clinical Trial Protocol

AEs will be assessed according to the CTCAE grade associated with the AE term. AEs that do not have a corresponding CTCAE term will be assessed according to their impact on the participant's ability to perform daily activities.

The possibility that the adverse event is related to study drug will be classified as one of the following: not related, unlikely, possible, probable, definite.

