9.2.2 Safety analysis

All operated patients will be included in safety analysis. Related AE and complications will be described.

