9.2.3 Analysis population

All operated patients will be included in analysis.

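### Section 4.3 item 2 makes unrelated 30-day death or morbidity a withdrawal reason, and the protocol does not settle whether such a patient stays in the efficacy analysis or whether unrelated events are described (minor)

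*Protocol*

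**What the plan says.** **Withdrawal.** Section 4.3 gives two criteria. The second covers "Patients developing mortality or morbidity during or within 30 days after the surgery that do not have consequential correlations with the surgical procedures". Its examples are disasters, wartime and accidents, introduced as illustrations and not as a closed list. The section does not say what happens to a withdrawn patient's data.

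**Endpoints.** Section 2.2.2 lists "Complication (rate, in 30 days) (intraoperative and/or postoperative) (Clavien system") with no condition on cause. Readmission, reoperation and mortality are listed over the same 30 days, also without one. Section 7 repeats these events, including "Perioperative mortality (in 30 days"). The primary endpoint (Sections 2.2.1 and 6) is completion of the operation without conversion, which is known on day 0.

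**Analysis sets.** The synopsis states "Efficacy assessment group: Per Protocol" and the protocol does not define that group. Section 9.2.3 states "All operated patients will be included in analysis". For safety, Section 9.2.2 states "All operated patients will be included in safety analysis".

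**Safety reporting.** Section 8.1 requires every adverse event after consent to go on the case report form, related or not. Section 9.2.2 commits to less: "Related AE and complications will be described". Section 8.1 grades attribution against a drug, although the product under study is a surgical system: "related to study drug will be classified as one of the following: not related, unlikely, possible, probable, definite".

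**The concern.** Withdrawal normally follows from something other than the outcome, such as refusal of follow-up, which is item 1. Item 2 is different. It selects operated patients on a post-operative event that falls in the same 30-day window as the secondary endpoints, and it does so through a causal judgement that those endpoints do not ask for.

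That would do no harm if the rest of the protocol fixed the consequence of withdrawal. In two places it does not.

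- **Primary endpoint.** A withdrawn patient is kept if Section 9.2.3 governs. The patient may be lost if the synopsis governs and withdrawal is taken to mean leaving the per-protocol group. A conversion or a completed operation already on record would then disappear because of an unrelated later event.
- **Described events.** Adverse events judged unrelated fall outside the commitment in Section 9.2.2. If the adjective there covers both nouns, complications judged unrelated fall outside it too.

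Both are choices that could be made after the events are known, in an open-label single-arm series of about 20 patients.

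**Working it through.** **1. The plan's own figure.** Section 3.1.1 plans 20 evaluable patients and allows for 5 screening failures and drop-outs: 20 + 5 = 25 enrolled. This reproduces and is not in dispute. The 25 includes screening failures, so 20 is used below as the number operated on. That is an assumption.

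**2. Route to the primary endpoint.**

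| Source | Who is analysed for efficacy | Patient withdrawn under item 2 |
|---|---|---|
| Synopsis | Per-protocol group, undefined | Could be dropped |
| Section 9.2.3 | Everyone operated on | Kept |

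Nothing in the protocol says which governs.

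**3. Size if one patient is dropped.** Let *x* be the successes among *n* operated patients.

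- Kept: *x*/*n*.
- Dropped patient had a conversion: *x*/(*n* − 1), a rise of *x*/[*n*(*n* − 1)].
- Dropped patient was a success: (*x* − 1)/(*n* − 1), a fall of (*n* − *x*)/[*n*(*n* − 1)].

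The protocol gives no expected success rate, so *x* is assumed. With *n* = 20 and *x* = 18, and exact Clopper-Pearson 95% intervals (lower limit: 2.5% point of Beta(*x*, *n* − *x* + 1); upper limit: 97.5% point of Beta(*x* + 1, *n* − *x*)):

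| Case | Rate | 95% CI |
|---|---|---|
| Kept | 18/20 = 90.0% | 68.3 to 98.8 |
| Conversion dropped | 18/19 = 94.7% | 74.0 to 99.9 |
| Success dropped | 17/19 = 89.5% | 66.9 to 98.7 |

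The changes are 18/(20 × 19) = 18/380 = +4.7 percentage points and −2/380 = −0.5 points.

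For a range, take *x* = 19. Then 19/20 = 95.0% becomes 19/19 = 100% (+19/380 = +5.0 points) or 18/19 = 94.7% (−1/380 = −0.3 points). With *x* = 20 there is no conversion to drop, and 19/19 is still 100%. So the shift runs from slightly down to about 5 points up, and is largest when the dropped patient is a conversion.

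**4. Route to the described events.** Section 8.1 records all adverse events. Section 9.2.2 keeps every operated patient in the denominator but promises a description of related events only.

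- If the adjective covers adverse events alone, unrelated adverse events need not be described and all complications are.
- If it covers both nouns, unrelated complications need not be described either.

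The sentence allows both readings. No rate is attached here, because the documents give no event frequencies.

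**The case against.** The strongest reply is that the protocol, read plainly, already protects the analysis. Sections 9.2.2 and 9.2.3 keep everyone operated on. Section 9.2.4 excludes only missing data, and a day-0 primary outcome is not missing. No passage says that withdrawal removes a patient from the per-protocol group, whose definition may sit in an analysis plan that is not shown. The clash between the synopsis and Section 9.2.3 would also exist without item 2. And item 2's examples suggest rare external causes, not ordinary post-operative morbidity.

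Most of this stands, and it limits the point to a small one. It does not remove it. The synopsis and Section 9.2.3 name different groups, and item 2 supplies a concrete reason for which the difference could matter. The list of examples is open, and morbidity is a broad word.

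A reader might infer more than the text supports:

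- *That 30-day deaths could vanish from the mortality rate.* Mortality is a separate endpoint with no relatedness condition. The sentence in Section 9.2.2 does not mention it, and every operated patient stays in the safety analysis.
- *That events would go unrecorded.* Section 8.1 requires them on the case report form whatever their cause.
- *That item 2 lets a death escape the termination rule.* Section 3.3, read plainly, counts deaths during the trial without regard to cause, and Section 4.3 does not say otherwise.
- *That the operating surgeon decides relatedness.* Section 13 says who operates the console. The protocol does not say who makes this judgement.

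**Conclusion.** The concern holds in a limited form, and its severity is minor. Item 2 attaches withdrawal to events that can themselves be 30-day endpoint events, on a relatedness test that those endpoints do not contain. The protocol contradicts itself on whether such a patient remains in the efficacy analysis, and it commits to describing fewer safety events than it records.

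The numerical effect is conditional. It needs an item-2 event to occur, the synopsis wording to prevail, and withdrawal to be read as exclusion. Under those assumptions one patient moves the success rate by about +4.7 or −0.5 percentage points at 18/20. If Section 9.2.3 governs, the success rate does not move. Safety denominators do not change under any of the readings set out here. The trial is descriptive with no formal testing (Section 9.1), so no test result or power is at stake.

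**What to change.** Four wording changes:

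1. **Section 4.3, item 2:** limit it to a reason for ending later study visits, and state that data already collected are kept and analysed.
2. **Synopsis:** replace the per-protocol efficacy group with all operated patients, to match Section 9.2.3.
3. **Section 9.2.2:** describe all adverse events and complications, with relatedness as a descriptive split. In Section 8.1, express relatedness to the procedure or device in place of the study drug.
4. **Sections 2.2.2 and 7:** state that all 30-day deaths, complications, readmissions and reoperations are counted regardless of cause.

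The cost is one short protocol amendment. No new data items are needed, because Section 8.1 already collects every adverse event with its attribution. The only other consequence is that the reported safety results may look slightly less favourable, since events judged unrelated will appear in them.

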5.1 Treatment administration

Under general anesthesia, the patient will be positioned according to indicated procedures described below [21]:

The patient will be placed in supine position. A rubber roll will be placed under the flank of disease site to create a minor body tilt. Incision will be made at the McBurney point of 3 cm size, 3 cm medial and 3 cm caudal to the anterior superior iliac spine. Access to retroperitoneal space will be built by dissection of subcutaneous fat and separation of muscles. SP Access Port or trocar will be inserted into the incision and oriented towards the reference anatomy. Depending on the availability, Custom Remote Center may be used. Dissection of the retroperitoneal fat tissue will be performed towards the posterior portion of the retroperitoneal cavity until the quadratus lumborum and medially the iliopsoas muscle are exposed. Then dissection of a plane just above the psoas muscle will allow identification of the ureter, which will be followed until renal pelvis and renal hilum seen. Standard steps of RNU will be followed thereafter. The axis of the patient's dissection will be pivoted to the patient's legs for BCR. Standard surgical treatment for UTUC includes not only excision of the ipsilateral kidney and the whole ureter, but also consisting of resection of the intramural portion of the ipsilateral ureter, which is the most distal part of the whole specimen, and the surgery includes closure of the bladder wall defect after the BCR, which nicely demonstrates the beauty of the reconstructive power of the da Vinci robotic system.

5.2 Concomitant therapy

Medical treatment of underlying chronic diseases (such as diabetes or hypertension) is allowed.

6. Efficacy Assessments

- Primary endpoint: Success without conversion to alternative surgery: successful completion of radical nephroureterectomy and bladder cuff resection with da Vinci SP system (no conversion to conventional laparoscopic, multiport da Vinci surgery or open surgery; addition of access port to complete the procedure would not be considered as conversion.)
- Operative time (min): first skin incision to closure of wound
- Console time (min): the time when the surgeon starts the console work till the specimen is taken out from the patient
- Estimated blood loss (mL): measured at operating suite
- Length of hospital stay (day): the duration from operation day to the discharge day (included)
- Pain score: measured by Visual Analogue Scale (VAS)

Other assessments:

- Patient demographics and medical history
- Pathology assessment
- Body mass index, body weight
- Analgesic use/types: opioid or non-opioid, changes in post-operative period)

Study: TASP-UTUC

Version: 1

Date: 17/10/2024

NTUH Clinical Trial Protocol

7. Safety Assessments

- Safety labs (complete blood count and other routine tests)
- Estimated blood loss (mL): measured at operating suite.
- Transfusion: record of blood product received.
- Complication (intraoperative and/or postoperative) (Clavien Dindo grading)
- Readmission (in 30 days)
- Reoperation (in 30 days)
- Perioperative mortality (in 30 days)

8. Adverse Event Reporting

Upon the occurrence of serious adverse events (SAE) which result in serious malfunctioning of the medical device, [name] [name] will report SAEs to the IRB of NTUH according to the Serious Adverse Event Reporting Procedures and Guidelines posted by NTUH. SAE reports to the IRB should include the following information when calling the Medical Monitor:

- Date and time of the SAE
- Date and time of the SAE report
- Name of reporter
- Call back phone number
- Affiliation/Institution conducting the study
- Protocol number
- Title of protocol
- Description of the SAE, including attribution to drug and expectedness

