8.2 Serious Adverse Events

ICH Guideline E2A and GCP of Taiwan define serious adverse events as those events, occurring at any dose, which meet any of the following criteria:

- Results in death
- Is life threatening (Note: the term life-threatening refers to an event in which the patient was at risk of death at the time of the event; it does not refer to an event which hypothetically might have caused death if it were more severe).
- Requires inpatient hospitalization (outside of planned combined treatment pathway) or prolongation of existing hospitalization
- Results in persistent or significant disability/incapacity
- Is a congenital abnormality/birth defect
- Events that may not meet these criteria, but which the investigator finds very unusual and/or potentially serious, will also be reported in the same manner.

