8.3 Adverse event follow-up

All AEs, including lab abnormalities that in the opinion of the investigator are clinically significant, will be followed according to good medical practices and documented as such. Site staff should send follow-up reports as requested when additional information is available. Additional information should be entered on the IRB of NTUH of SAE form in the appropriate format. Follow-up information should be sent to NTUH IRB as soon as possible according to IRB's Serious Adverse Event Reporting Procedures and Guidelines.

9. Statistical Considerations

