9.2.4 Missing, non-compliance, and others

Analysis will be carried on for available data after exclusion of the missing data.

If deviation(s) from the original statistical plan is identified, the investigator will follow the guideline of IRB to record and report such incident. The PI will report to IRB for with further review.

10. Direct Access to Source Data/Documents

Investigators permit IRB to access to the source data of experiment for trial-related monitoring, audits and regulatory inspection.

11. Ethical Considerations

This study will be conducted according to Taiwan and international standards of Good Clinical Practice for all studies. Applicable government regulations and NTUH research policies and procedures will also be followed.

This protocol and any amendments will be submitted to the NTUH Research Ethics Committee / Institutional Review Board (IRB) for formal approval to conduct the study. The decision of the IRB concerning the conduct of the study will be made in writing to the investigator.

All subjects for this study will be provided a consent form describing this study and providing sufficient information for subjects to make an informed decision about their participation in this study. This consent form will be submitted with the protocol for review and approval by the IRB. The formal consent of a subject, using the IRB-approved consent form, will be obtained before that subject is submitted to any study procedure. This consent form must be signed by the subject or legally acceptable surrogate, and the investigator-designated research professional obtaining the consent.

12. Data Handling and Keeping

The investigator shall accurately collect, record and report all data resulting from its conduct of the study in the manner, and pursuant to the schedule, set forth in the protocol. The investigators and the research assistants of this study will handle the research data. Clinical information, surgical image and parameters will be collected in NTUH. The data will be stored in computers of laboratory with an electronic encryption and in compliance with applicable regulations and regulatory agency requirements. The clinical and source data can only be assessed by clinical doctors and investigators of the study and kept for at least 5 years after the end of this study. A monitor may be appointed by NTUH and the investigator and who will be responsible for monitoring and reporting on the progress of the

Study: TASP-UTUC

Version: 1

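### Section 8's only explicit trigger for a first SAE report to the IRB is tied to a device malfunction, while section 8.2 defines SAEs by patient outcome and presupposes that all of them are reported

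*Protocol*

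**What the plan says.** Section 8 of the Protocol begins the reporting duty with the condition "Upon the occurrence of serious adverse events (SAE) which result in serious malfunctioning of the medical device". In that case a named individual reports SAEs to the IRB of the hospital under its posted SAE procedures. The next sentence lists what an SAE report to the IRB should contain and repeats no device condition.

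Section 8.1 requires all adverse events after consent to be recorded on the case report form. One of the data items is whether the event was reported as an SAE.

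Section 8.2 defines an SAE by what happens to the patient: death, threat to life, hospitalization or its prolongation, lasting disability, or birth defect. It closes with "Events that may not meet these criteria, but which the investigator finds very unusual and/or potentially serious, will also be reported in the same manner".

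Section 8.3 adds, for later information: "Follow-up information should be sent to NTUH IRB as soon as possible according to IRB's Serious Adverse Event Reporting Procedures and Guidelines".

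On the IRB's role, section 3.3 says "The trial shall be terminated by the investigator or the IRB when deemed necessary after evaluation" and then "Incidents that may cause the termination of the trial include the encounter of life-threatening AE, fatal AE, serious non-compliance, etc".

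**The concern.** The condition in section 8 and the definition in section 8.2 do not cover the same events. The first depends on the device, the second on the patient. The risks that the protocol itself expects from the operation belong mainly to the second kind. Section 1.3 lists "Perioperative risks related to the surgeries: bleeding, wound infection, adjacent organ injury, wound dehiscence". Any of these can become serious in the sense of 8.2 while the device works as intended.

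The stake is IRB oversight. Section 3.3 gives the IRB its own power to end the trial. The IRB can act promptly on a fatal or life-threatening event only if someone tells it, and a follow-up report under 8.3 assumes that a first report has already been made. Section 9.1 describes the system as pre-market, and the synopsis plans no interim analysis, so prompt notice of single events matters here.

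**Working it through.** No arithmetic applies. The check is whether any other part of the Protocol supplies the first-report trigger that section 8 appears to restrict.

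| Place | What it requires | First SAE report to the IRB? |
|---|---|---|
| Section 8, opening sentence | Report to the IRB when an SAE leads to a device malfunction | Yes, with the device condition |
| Section 8, next sentence | Contents of an SAE report | No; it describes a report but does not say when one is due |
| Section 8.1 | Recording of all adverse events on the case report form | No |
| Section 8.2, outcome criteria | Definition of an SAE | No |
| Section 8.2, closing item | Events outside the criteria are reported as well, in the same way | Only for events outside the criteria, with no recipient named |
| Section 8.3 | Follow-up information to the IRB | No; it presupposes a first report |
| Section 3.3 | Written explanation to the IRB after termination | No |
| Section 1.4 | Reporting of protocol deviations | No |
| Section 9.2.4 | Reporting of deviations from the statistical plan | No |
| Section 10 | IRB access to source data | No; it gives access, not notice |

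**Step 1.** Section 8 is therefore the only place that says when a first SAE report goes to the IRB.

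**Step 2.** None of the outcome criteria in 8.2 mentions the device. The closing item extends reporting to events that fall short of the criteria. An extension of that kind is meaningful only if events that meet the criteria are already reported, so 8.2 presupposes reporting of every SAE.

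**Step 3.** Taken at its word, section 8 then gives an odd ordering. An event that is merely very unusual is reported through the closing item of 8.2. A postoperative death with a working device meets the first criterion of 8.2 but not the condition in section 8, so it has no stated first report.

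**Step 4.** The condition also runs in the wrong direction. It has the patient's event produce the malfunction. A malfunction can harm a patient, but a patient event does not ordinarily cause a malfunction. This points to a drafting error rather than a deliberate limit. Reversing cause and effect would not remove the mismatch, because the trigger would still depend on a malfunction.

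**The case against.** The passages can be read together. Section 8 does not say that only these SAEs are reported, and no passage says that others are not. The sentence on report contents is unqualified, 8.1 asks of every event whether it was reported as an SAE, and 8.3 speaks of SAE follow-up without a device condition. Section 1.4 commits the trial to conduct "according to Good Clinical Practice standards and per Taiwan Health Authority regulations", and section 11 adds "Applicable government regulations and NTUH research policies and procedures will also be followed". The hospital procedures cited in section 8 may require every SAE to be reported. The literal reading would cover almost nothing, so staff may never apply it. Section 10 also gives the IRB access to source data.

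Most of this stands, and it limits the point. The conflict is implied, and the general commitments favour the wider reading. But a general commitment does not correct a specific sentence that says something narrower, and section 8 invokes the hospital procedures inside that same sentence. Access to source data lets the IRB look; it does not tell the IRB promptly that something has happened.

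Two stronger readings are tempting. A reader might infer that SAEs without a malfunction would in fact go unreported. The document does not show this, because the governing procedures are not reproduced. A reader might also infer that the stopping rule in 3.3 (2 mortalities or 5 severe morbidities) would fail. It would not: the investigator applies that rule, and it does not depend on section 8.

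**Conclusion.** The point holds as a mismatch between a reporting trigger and a definition, and it should be fixed. Section 8 carries the only explicit trigger for a first IRB report and words it as a garbled device condition, while 8.2 assumes that every SAE by patient outcome is reported. Followed literally, deaths, life-threatening events and prolonged hospitalizations without a malfunction lack a stated first report.

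The effect is confined to the IRB reporting route. Recording under 8.1 covers all adverse events, the safety analysis in 9.2.2 takes in all operated patients, and the primary endpoint is completion of the operation without conversion; none of these uses the section 8 trigger. The number of reports affected cannot be estimated from the document. The conclusion assumes only that the Protocol text is read as written. Whether practice at the hospital would differ depends on procedures that are not shown.

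**What to change.** Reconcile section 8 with 8.2 by replacing the opening condition with a sentence such as: *Any SAE as defined in 8.2, whether or not it is associated with a device malfunction, will be reported to the IRB of NTUH under the hospital's SAE reporting procedures and guidelines.* Check the sentence against those procedures before the amendment is filed. Sections 8.1 and 8.3 then need no change on this point.

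The cost is a one-sentence amendment and possibly some additional reports to the IRB. If the hospital's procedures already require all SAEs to be reported, there would be no additional reports, and the change only brings the Protocol into line with them.
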